#### **2.1.4 Benefit:Risk Assessment**

Novavax has collected safety, efficacy, and immunogenicity data from approximately 50,000 participants across 5 clinical trials, including 2 independent Phase 3 trials in the US/Mexico (Study 2019nCoV-301) and the UK (Study 2019nCoV-302). The data from these trials, along with supporting preclinical studies, indicate that the known and potential benefits of the vaccine outweigh its known and potential risks.

Myocarditis or pericarditis has been reported following vaccination with NVX-CoV2373 in clinical trials, and it is possible that these reports represent vaccine-associated adverse events similar to those associated with mRNA COVID-19 vaccines. While available data may not be sufficient to definitively establish a causal relationship with NVX-CoV2373, neither can a causal relationship be excluded.

Myocarditis or pericarditis associated with mRNA vaccines has been reported in greatest numbers in males under the age of 30 years following a second dose, but cases have been reported in older males and in females as well, and also following the first dose. While some cases require intensive care support, available data from short-term follow-up suggest that most individuals have had resolution of symptoms with conservative management. Information is not yet available about potential long-term sequelae.

The CDC has published clinical considerations for myocarditis and pericarditis after receipt of mRNA COVID-19 vaccines among adolescents and young adults [CDC 2021] which makes specific recommendations for the management of such cases. A surveillance and management plan for suspected myocarditis and/or pericarditis cases based on CDC and AHA recommendations [CDC 2021, Law 2021, Gargano 2021] has been implemented in the clinical development plan of NVX-CoV2373.

#### **Study Rationale**

Novavax, Inc. has developed a recombinant vaccine adjuvanted with the saponin-based Matrix-M adjuvant for the prevention of disease caused by SARS-CoV-2 (NVX-CoV2373). Both nonclinical and clinical data to date support continued clinical development of SARS-CoV-

2 recombinant spike protein nanoparticle vaccines (SARS-CoV-2 rS) combined with Matrix-M adjuvant as potential vaccines against SARS-CoV-2.

The purpose of this study is to compare the immunogenicity and safety of 3 different lots of NVX-CoV2373 in previously vaccinated adult participants 18 to 49 years of age, inclusive. Data from the study are intended to support the overall manufacturing data submitted as part of the Biological License Application in the United States and as part of other Regulatory submissions in other countries.

### 3 OBJECTIVES AND ENDPOINTS

The purpose of this study is to compare the immunogenicity and safety of 3 different lots of NVX-CoV2373 in previously vaccinated adult participants 18 to 49 years of age, inclusive.

An overview of all study objectives and endpoints is provided in [Table 2](#).

**Table 2 Study 2019nCoV-307 Objectives and Endpoints**

	Objectives	Endpoints
Primary	To demonstrate the equivalence of 3 different vaccine lots based on IgG responses.	IgG geometric mean ELISA unit (GMEU) concentrations (ie, GMEU/mL) to the SARS-CoV-2 spike protein at Day 29 in each treatment arm; equivalence will be demonstrated if the 95% confidence intervals [CIs] of GMEU concentrations for all pairs of lots are within the pre-specified equivalence range of 0.67 to 1.5 GMEU/mL.
Secondary	To characterize the IgG antibody responses to 3 different lots of NVX-CoV2373.	Proportion of participants in each treatment arm who achieve seroconversion ( $\geq$ 4-fold increase from baseline) in IgG concentrations to the SARS-CoV-2 spike protein at Day 29.
	To characterize the neutralizing antibody responses to 3 different lots of NVX-CoV2373.	
 
• MN50 geometric mean titers to the SARS-CoV-2 spike protein at Day 29 in each treatment arm.
 
• Proportion of participants in each treatment arm who achieve seroconversion (<math>\geq</math> 4-fold increase from baseline) in MN50 titers to the SARS-CoV-2 spike protein at Day 29.
 

	To characterize antibody responses in a human angiotensin-converting enzyme 2 (hACE2) receptor binding inhibition assay to the SARS-CoV-2 spike protein in participants vaccinated with 3 different lots of NVX-CoV2373.	
 
• hACE2 inhibition assay titers (geometric mean titer [GMTs]) at Day 29 in each treatment arm
 
• Proportion of participants in each treatment arm who achieve seroconversion (<math>\geq</math> 4-fold increase from baseline) in hACE2 titers concentrations to the SARS-CoV-2 spike protein at Day 29.
 

[figure not shown]
**Table 2 Study 2019nCoV-307 Objectives and Endpoints**

	Objectives	Endpoints
	To compare the overall safety of 3 different lots of NVX-CoV2373.	
 
• Incidence, duration, severity, and relationship of MAAEs and AESIs (including myocarditis and/or pericarditis) through Day 29 (ie, 28 days after vaccine dose).
 
• Incidence and relationship of SAEs throughout the study.
 

Exploratory	To utilize additional assays (current or to be developed) to best characterize the immune response for future vaccine development needs.	Additional endpoints to compare immune responses may be developed based on the assays used.

## 4 STUDY PLAN

### 4.1 Study Schematic

**Figure 1 Flow Diagram for 2019nCoV-307**

Abbreviations: EOS = end of study

### 4.2 Study Design

This is a randomized, Phase 3 study comparing the immunogenicity and safety of 3 different lots of NVX-CoV2373. The study will enroll approximately 900 previously vaccinated adults 18 to 49 years of age, inclusive.

Participants will be screened at baseline with the goal of enrolling approximately 900 previously vaccinated participants. Participants will be randomized 1:1:1 to receive 1 dose of the vaccine from 1 of 3 different lots, given on Day 1, at a dose level of 5 µg of antigen with 50 µg of Matrix-M adjuvant.

All participants will remain on study for immunogenicity and safety data collection through 28 days following the vaccination.

### 4.3 Design Rationale

Novavax, Inc. has developed a recombinant vaccine adjuvanted with the saponin-based Matrix-M adjuvant for the prevention of disease caused by SARS-CoV-2 (NVX-CoV2373).

The purpose of this study is to compare the consistency of immunogenicity and safety of the 3 different lots of NVX-CoV2373 in previously vaccinated adult participants 18 to 49 years of age. Data from the study are intended to support the overall manufacturing consistency data submitted as part of regulatory submissions in the US and elsewhere, as needed.

## **5 POPULATION**

### **5.1 Recruitment**

Approximately 1200 potential participants will be screened in order to meet the goal of 900 randomly assigned participants, who will be further divided into 3 groups of 300 participants each.

### **5.2 Definitions**

Participants officially enter the Screening Period following provision of informed consent.

A screen failure is a consented participant who has been deemed ineligible on the basis of one or more eligibility criteria or who has withdrawn consent prior to treatment assignment. Screen failures may not be rescreened.

An enrolled participant is one who has been deemed eligible and has been assigned to a treatment group.

### **5.3 Inclusion Criteria**

To be included in this study, each individual must satisfy all of the following criteria:

1. Adults 18 to 49 years of age, inclusive, at screening.
2. Willing and able to give informed consent prior to study enrollment and to comply with study procedures.
3. Participants of childbearing potential (defined as any participant who has experienced menarche and who is NOT surgically sterile [ie, hysterectomy, bilateral tubal ligation, or bilateral oophorectomy] or postmenopausal [defined as amenorrhea at least 12 consecutive months]) must agree to be heterosexually inactive from at least 28 days prior to enrollment and through the end of study (EOS) visit OR agree to consistently use a medically acceptable method of contraception from at least 28 days prior to enrollment and through the EOS visit.
4. Is medically stable, as determined by the investigator (based on review of health status, vital signs [to include body temperature], medical history, and targeted physical examination [to include body weight]). Vital signs must be within medically acceptable ranges prior to the study vaccination.
5. Agree to not participate in any other SARS-CoV-2 prevention or treatment trials for the duration of the study. Note: For participants who become hospitalized with COVID-19, participation in investigational treatment studies is permitted.
6. Documented receipt of either 2 or 3 doses of the investigational Novavax vaccine with Matrix-M adjuvant (NVX-CoV2373); OR documented receipt of a full course of an FDA-authorized/approved COVID-19 vaccine with or without a booster vaccine injection after primary series; OR documented receipt of a full course of heterologous COVID-19 vaccines mentioned above. The most recent dose must have been administered at least 6 months prior to study vaccination.

#### 5.4 Exclusion Criteria

Participants meeting any of the following criteria will be excluded from the study.

1. History of laboratory-confirmed (by polymerase chain reaction [PCR] or rapid antigen test) COVID-19 infection  $\leq 4$  months prior to randomization.
2. Current participation in research involving receipt of an investigational product (drug/biologic/device).
3. Any known allergies or history of anaphylaxis to the active substance or any of the other ingredients contained in the investigational product.
4. Any autoimmune or immunodeficiency disease/condition (iatrogenic or congenital) or therapy that causes clinically significant immunosuppression.
5. Received any vaccine  $\leq 90$  days prior to study vaccination, except for influenza vaccine which may be received  $> 4$  days prior to study vaccine, or rabies vaccine which may be received at any time if medically indicated.
6. Received immunoglobulin, blood-derived products, or immunosuppressant drugs within 90 days prior to study vaccination, except for rabies immunoglobulin which may be given if medically indicated.
7. Active cancer (malignancy) on chemotherapy that is judged to cause significant immunocompromise within 1 year prior to first study vaccination (with the exception of malignancy cured via excision, at the discretion of the investigator).
8. Participants who are breastfeeding, pregnant, or who plan to become pregnant prior to the EOS visit.
9. Suspected or known history of alcohol abuse or drug addiction within 3 months prior to the study vaccine dose that, in the opinion of the investigator, might interfere with protocol compliance.
10. Any other condition that, in the opinion of the investigator, would pose a health risk to the participant if enrolled or could interfere with evaluation of the trial vaccine or interpretation of study results (including neurologic or psychiatric conditions likely to impair the quality of safety reporting).
11. Study team member or immediate family member of any study team member (inclusive of Sponsor, clinical research organization [CRO], and study site personnel involved in the conduct or planning of the study).
12. Participants with a history of myocarditis or pericarditis.

## **6 STUDY CONDUCT**

This is a Phase 3, randomized, study comparing the immunogenicity and safety of different lots of NVX-CoV2373. In this study, approximately 900 previously vaccinated adults 18 to 49 years of age will receive 1 dose of NVX-CoV2373 from 3 different lots, given on Day 1.

Following vaccination, all participants will remain on study for immunogenicity and safety data collection through Day 29 (EoS). Scheduled study visits will occur for Screening, Day 1, and Day 29.

### **6.1 Study Procedures by Visit**

#### **6.1.1 Screening Period**

The following activities will occur at the Screening Visit. The Screening Visit can be and is expected to be combined with the Day 1 Visit.

- Informed consent
- Medical history, including prior and concurrent medical conditions and significant surgical procedures.
- Inclusion and exclusion criteria
- Demographics including age, sex, race, and ethnicity.
- Prior and concomitant medications, including recent ( $\leq 90$  days) and current medications and vaccinations, are to be reviewed to ensure eligibility criteria are fulfilled. Concomitant medications include prescription and OTC (including vaccines) medications taken by the participant during the study. Do not record herbals, vitamins, and supplements.
- Vital sign measurements including respiratory rate, blood pressure, pulse rate, and temperature (oral or via forehead/ear reader). Urine pregnancy test in women of childbearing potential. A positive test will result in screen failure.
- Physical examination at screening to include height and weight, head nose ears and throat (HEENT), neck, lungs, heart, cardiovascular, abdomen, and musculoskeletal system/extremities to allow for study vaccination.
- Recording of SAEs.

#### **6.1.2 Vaccine Administration Period (Day 1)**

The following activities will occur at the Day 1 visit.

- Inclusion and exclusion criteria
- Prior/concomitant medications
- Vital sign measurements, including respiratory rate, blood pressure, pulse rate, and temperature (oral or via forehead/ear reader). Temperature will be taken prior to vaccination to ensure participant has no evidence of fever.
- Urine pregnancy test in women of childbearing potential. A positive test will result in disqualification.
- Baseline ECG
- Physical examination – symptom directed (targeted) if Screening and Day 1 are not combined into a single visit

- Nasal swab at clinic for SARS-CoV-2 (PCR)—anterior nares
- Blood sampling for SARS-CoV-2 (ELISA for anti-S protein serology, MN50 assay, and hACE2 receptor-binding inhibition assay)
- Randomization
- Vaccination
- Recording of SAEs, MAAEs, and AESIs (including potential immune-mediated medical conditions [PIMMCs] and myocarditis or pericarditis). See [Table 4](#) for symptoms of myocarditis or pericarditis and Section [8.2.3.6](#) for instructions for follow-up.
- Participants will remain in the clinic or under study staff observation for at least 15 minutes post-vaccination to be monitored for any immediate hypersensitivity reactions.

### 6.1.3 Unscheduled Visit

An Unscheduled Visit may be conducted by study personnel for safety follow-up for any participant experiencing a general medical issue while on study. During this visit, the following procedures will be performed:

- Prior/concomitant medications
- Vital sign measurements including respiratory rate, blood pressure, pulse rate, and temperature (oral or via forehead/ear reader).
- Physical examination – symptom directed (targeted)
- Recording of SAEs, MAAEs, and AESIs (including PIMMCs, myocarditis or pericarditis). See [Table 4](#) for symptoms of myocarditis or pericarditis and Section [8.2.3.6](#) for instructions for follow-up.

NOTE: Blood sample collection and other optional testing may be performed during an Unscheduled Visit if directed by the Investigator for clinical evaluation of an AE.

### 6.1.4 EOS (Day 29)

The following activities will be performed at the EOS Visit. EOS assessments will be conducted via an on-site visit.

- Prior/concomitant medications
- Vital sign measurements including respiratory rate, blood pressure, pulse rate, and temperature (oral or via forehead/ear reader).
- Physical examination – symptom directed (targeted)
- Blood sampling for SARS-CoV-2 (ELISA for anti-S protein serology, MN50 assay, and hACE2 receptor-binding inhibition assay)
- Recording of SAEs, MAAEs, and AESIs (including PIMMCs, myocarditis or pericarditis). See [Table 4](#) for symptoms of myocarditis or pericarditis and Section [8.2.3.6](#) for instructions for follow-up.

---

## **6.2 Discontinuation or Withdrawal**

### **6.2.1 Withdrawal from Study**

Participants are free to withdraw from the study at any time upon request. Participant participation in the study may be stopped at any time at the discretion of the Investigator or at the request of the Sponsor.

Participants may refuse further procedures but are encouraged to remain in the study for safety follow-up. In such cases, where only safety is being evaluated, participant contact may be managed via telemedicine contact (eg, telephone, web chat, video, FaceTime).

#### **6.2.1.1 Replacement of Participants**

Participants who withdraw, are withdrawn or terminated from this study, or are lost to follow up after signing the informed consent form (ICF) but prior to study vaccination may be replaced. Participants who receive study vaccine and subsequently withdraw, discontinue, are terminated from the study, or are lost to follow-up will not be replaced.

#### **6.2.1.2 Participants Lost to Follow-up**

Whenever possible, any participant who withdraws from the study prematurely will undergo all EOS assessments. Any participant who fails to return for final assessments will be contacted by the site in an attempt to have them comply with the protocol.

All reasonable efforts, including contact of emergency contact, must be made to locate participants to determine and report their ongoing status. Lost to follow-up is defined by the inability to reach the participant after a minimum of 3 documented phone calls, text messages, faxes, or emails (not performed on the same day), as well as a lack of response by the participant to one registered mail letter. All attempts should be documented in the participant's source documents and/or medical records. If it is determined that the participant has died, the study site will use permissible local methods to obtain the date and cause of death and as much other information as can be obtained, including post-mortem reports.

The status of participants who fail to complete final assessments will be documented in the electronic case report form (eCRF). Data that would have been collected at subsequent visits will be considered missing.

## **6.3 Study Termination by Sponsor**

Although the Sponsor has every intention of completing the study, it reserves the right to discontinue it at any time for clinical or administrative reasons.

The EOS is defined as the date on which the last participant completes the last study visit (including the EOS visit). Any additional long-term follow-up that is required for monitoring of the resolution of an AE or finding may be appended to the clinical study report (CSR).

## 7 STUDY INTERVENTIONS

Study vaccinations will comprise 1 IM injection of NVX-CoV2373 of 0.5 mL injection volume at a dose of 5 µg antigen ([Table 3](#)).

**Table 3 Study Vaccinations**

Vaccine	Age (years)	Baseline Serostatus	Number of doses	Number of participants	Dose (antigen/ Matrix-M adjuvant)
Lot 1 (Group 1)	18 to 49	Previously vaccinated	1	300	5 µg / 50 µg
Lot 2 (Group 2)	18 to 49	Previously vaccinated	1	300	5 µg / 50 µg
Lot 3 (Group 3)	18 to 49	Previously vaccinated	1	300	5 µg / 50 µg

### 7.1 Description of Products

#### 7.1.1 NVX-CoV2373

##### 7.1.1.1 Formulation, Storage, Preparation, and Handling

NVX-CoV2373 Prototype SARS-CoV-2 rS vaccine will be supplied as a solution for preparation for injection of SARS-CoV-2 rS at a concentration of 10 µg/mL and Matrix-M adjuvant at a concentration of 100 µg/mL.

NVX-CoV2373 should be stored at 2 to 8°C in a secured location. DO NOT FREEZE. The study site will maintain a temperature log to establish a record of compliance with storage conditions.

Further details on the trial vaccine can be found in the SARS-CoV-2 rS IB and a description of its preparation can be found in the Pharmacy Manual.

##### 7.1.1.2 Packaging and Labeling

The Sponsor will provide adequate quantities and appropriate labelling of SARS-CoV-2 rS with Matrix-M adjuvant and Syneos Health will ensure distribution to the study sites from a designated depot. The clinical unit pharmacy or equivalent will prepare the clinical trial materials. Detailed instructions for the handling of trial vaccine vials will be provided in a separate Pharmacy Manual.

##### 7.1.1.3 Dosing and Administration

The vaccine should be drawn into a syringe on the day of administration by a qualified member of study site personnel, and the vaccine should be administered according to standard practice by qualified study site personnel in a way to maintain overall blinding, as described in the Pharmacy Manual.

All participants will be administered 1 single IM injection of NVX-CoV2373 of 0.5 mL injection volume on Day 1.

#### 7.1.1.3.1 Study Vaccination Pause Rules

Study vaccination will be paused in the event of reports of 2 or more events of probable or confirmed pericarditis or myocarditis ([Table 4](#)), pending review of cases by the Central Cardiac Adjudication Committee that will report the results of their adjudication to the Sponsor to recommend whether enrollment may be resumed.

### 7.1.2 Treatment Assignment and Bias Minimization

#### 7.1.2.1 Treatment Allocation

An Interactive Web Response System (IWRS) will be responsible for the allocation of randomization numbers to individual participants. A copy of the randomization code with true treatment allocations will be held by Syneos Health during the study. Another randomization list (containing treatment) will be provided to clinical supplies.

#### 7.1.2.2 Assessment and Verification of Compliance

Study vaccine should be administered in the clinical unit under direct observation of clinic personnel and recorded in the eCRF. Clinic personnel will confirm that the participant has received the entire dose.

The location (right or left arm, or other location if required), if the full dose was administered, date, and timing of all doses of study vaccine will be recorded in the participants' eCRF. If a participant is not administered study vaccine, the reason for the missed dose will be recorded.

#### 7.1.2.3 Blinding

This is an observer-blinded study. To maintain the blind, unblinded study site personnel will manage vaccine logistics, preparation, and administration according to the Pharmacy Manual so as to maintain the blind from the remainder of the study site personnel and participants. The unblinded study site personnel may administer study vaccine if qualified to do so, but will not be involved in study-related assessments or have participant contact for data collection after administration of trial vaccine.

Within each study site, participants will be assigned to study treatment according to a list produced by Syneos Health. Prior to production, the randomization specification will be reviewed and agreed by the study team.

An IWRS will be responsible for the allocation of randomization numbers to individual participants. Randomization will take place at baseline after confirmation that the participant meets the inclusion/exclusion criteria. A copy of the randomization code with true treatment allocations will be held by Syneos Health during the study. Another randomization list (containing treatment) will be provided to clinical supplies.

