Number of Sites	Approximately 30 sites in the US
Study Duration	Estimated duration: 1 Month (excluding screening)

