### **9.1 Sample Size Rationale**

The sample size and power are driven by the primary endpoint (ie, lot consistency in terms of immunogenicity measured by IgG response at Day 29). Based on IgG data from Novavax's study 2019nCoV-101 Part 2, previously vaccinated participants in the 18-49-year-old age group who received the SARS-CoV-2 rS vaccine, exhibited an 80% confidence upper bound of Day 29 IgG SD in log10 scale of 0.39. The immunogenic performance of the released lots should be approximately the same, ie, the lot-to-lot GMEU ratio should approximate 1.0. Under any manufacturing practices, between-lot variation exists and is considered normal. Assuming 10% variation (lot-to-lot GMEU ratio is 1.1), an evaluable sample size of 248 subjects for each lot in the per-protocol population will be required to achieve 97% power to demonstrate the lot-to-lot equivalence and provide the overall power of ~90% for all three lot-to-lot equivalence tests (Lot 1 vs. Lot 2, Lot 1 vs. Lot 3, and Lot 2 vs. Lot 3). Accounting for a ~5% dropout rate, a total enrollment sample size of 300 participants will provide 262 participants per lot.

The statistical success criterion for demonstrating the equivalence of each lot (Lot 1, Lot 2, and Lot 3) is based on the IgG response at Day 29. Equivalence will be demonstrated if the 95% CIs of GMEUs for all pairs of lots are within the pre-specified equivalence range of 0.67 to 1.5.

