#### 9.3.2 Immunogenicity Analyses

The immunogenicity analysis will be performed using the PP Analysis Set.

For the primary endpoint of IgG (GMEU/mL) to the SARS-CoV-2 spike protein in previously vaccinated participants 18 to 49 years of age, IgG GMEU, geometric mean fold rise ( $\text{GMFR}_{\text{Post/Pre}}$ ), and SCR will be summarized overall and by study vaccine group.

IgG GMEU is calculated as the antilog of the mean of the log-transformed IgG GMEU at Days 1 and 29.  $\text{GMFR}_{\text{Post/Pre}}$  is calculated as the ratio of post-vaccination IgG GMEU at Day 29 to pre-vaccination IgG GMEU at the baseline (Day 1).

Between-group ratio of IgG GMEUs (GMEUR) at Day 29 and the two-sided 95% CIs will be computed using analysis of covariance (ANCOVA), with the study vaccine group as the fixed effect and the ELISA unit at Day 1 (adjusted for intergroup variation in baseline [pre-vaccination] ELISA unit) as the covariate under two-sided type I error rate of 0.05. No type I error rate adjustments will be made. The mean difference of all lots paired comparisons with their corresponding CI limits will then be exponentiated to obtain IgG GMEUR and the corresponding 95% CIs.

As the 1st secondary endpoint of IgG GMEUs (EU/mL) to the SARS-CoV-2 spike protein, SCR (proportion of participants who achieve seroconversion  $\geq 4$ -fold increase from baseline) in IgG GMEUs at Day 29 with corresponding two-sided exact binomial 95% CIs will be calculated using the Clopper-Pearson method. Two-sided 95% CIs of the difference in SCRs in IgG GMEU concentrations for all lots paired comparisons will be based on the Miettinen and Nurminen method.

For the 2nd secondary endpoints of neutralizing antibody response to 3 different lots of NVX-CoV2373 in previously vaccinated participants 18 to 49 years of age, MN50 GMT, GMFRPost/Pre, and SCR will be summarized overall and by the study vaccine group.

MN50 GMT is calculated as the antilog of the mean of the log-transformed MN50 titers at Days 1 and 29. GMFR is calculated as the ratio of post-vaccination MN50 GMTs at Day 29 to pre-vaccination MN50 GMTs at the baseline (Day 1).

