1.2 Sample Size Rationale

The sample size and power are driven by the primary endpoint (ie, lot consistency in terms of immunogenicity measured by IgG response at Day 29). Based on IgG data from Novavax's study 2019nCoV-101 Part 2, previously vaccinated participants in the 18-49-year-old age group who received the SARS-CoV-2 rS vaccine, exhibited an 80% confidence upper bound of Day 29 IgG SD in log10 scale of 0.39. The immunogenic performance of the released lots should be approximately the same; ie, the lot-to-lot GMEU ratio should approximate 1.0. Under any manufacturing practices, between-lot variation exists and is considered normal. Assuming 10% variation (lot-to-lot GMEU ratio is 1.1), an evaluable sample size of 248 subjects for each lot in the per-protocol population will be required to achieve 97% power to demonstrate the lot-to-lot equivalence and provide the overall power of ~90% for all three lot-to-lot equivalence tests (Lot 1 vs. Lot 2, Lot 1 vs. Lot 3, and Lot 2 vs. Lot 3). Accounting for a ~5% dropout rate, a total enrollment sample size of 300 participants will provide 262 participants per lot.

The statistical success criterion for demonstrating the equivalence of each lot (Lot 1, Lot 2, and Lot 3) is based on the IgG response at Day 29. Equivalence will be demonstrated if the 95% CIs of GMEUs for all pairs of lots are within the pre-specified equivalence range of 0.67 to 1.5.

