1.3 Randomization Strategy and Procedure

An Interactive Web Response System (IWRS) will be responsible for the allocation of randomization numbers to individual participants. Participants will be randomized in a 1:1:1 ratio to receive one of 3 lots of the study vaccine.

A copy of the randomization code with true treatment allocations will be held by Syneos Health during the study. Another randomization list (containing treatment) will be provided to clinical supplies.

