7.1.1 ELISA (IgG) ELISA Units for SARS-CoV-2

As the primary objectives, IgG GMEUs (EU/mL) to the SARS-CoV-2 spike protein in previously vaccinated participants 18 to 49 years of age, the derived/calculated endpoints of IgG response will include:

- IgG GMEU is calculated as the antilog of the mean of the log-transformed IgG GMEU at Days 1 and 29. IgG GMEU will be summarized by the study vaccine group and visit day along with the corresponding 2-sided 95% CIs, by exponentiating the corresponding log-transformed means and their 95% CIs.
- $GMFR_{Post/Pre}$ is calculated as the ratio of post-vaccination IgG GMEU at Day 29 to pre-vaccination IgG GMEU at the baseline (Day 1).
 - IgG $GMFR_{Post/Pre}$ for each study vaccine group will be conducted using paired t distribution. A sample SAS code is given below to estimate IgG $GMFR_{Post/Pre}$ and corresponding 95% CIs.

```
proc means data=IgG_D1andD29_nonmissing n mean std t prt clm;  
    var diff_aval;  
    output out=paired N=n MEAN=mean STDERR=stderr STD=stddev  
        LCLM=lclm UCLM=uclm prt=prt;  
run;
```

- IgG GMEUR between any two of study vaccine groups at Day 29 and the two-sided 95% CIs will be computed using analysis of covariance (ANCOVA), with the study vaccine group as the fixed effect and IgG ELISA unit at Day 1 (adjusted for intergroup variation in baseline [pre-vaccination] IgG ELISA unit) as the covariate under two-sided type I error rate of 0.05. No type I error rate adjustments will be made. The mean difference of all lots paired comparisons with their corresponding CI limits will then be exponentiated to obtain IgG GMEUR and the corresponding 95% CIs.
 - Sample SAS code for GMEUR for all pairwise comparisons (Group 1 vs. Group 2, Group 1 vs. Group 3, and Group 2 vs. Group 3) is given below:

```
proc mixed data=IgG;  
    class Group;  
    model log(IgG) = log(IgG_D0) Group;  
    lsmeans Lot/cl diff e alpha=0.05;  
run;
```

As the 1st secondary objectives, IgG GMEUs (EU/mL) to the SARS-CoV-2 spike protein in previously vaccinated participants 18 to 49 years of age, the derived/calculated endpoints of IgG response will include:

- SCR is defined as proportion of participants who achieve seroconversion ≥ 4 -fold increase from baseline in IgG GMEUs at Day 29. SCR in IgG GMEUs with

corresponding two-sided exact binomial 95% CIs will be calculated using the Clopper-Pearson method with the following sample SAS code:

```
proc freq data=IgG noprint;
    by Group;

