11.2 Adjustments for Covariates

GMTR/GMEUR between the study vaccine groups for all pairwise comparisons will be adjusted for pre-vaccination titer/ELISA unit.

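### Lots are assigned within site but the primary ANCOVA has no site term, so the equivalence intervals may be slightly wider than needed

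*Protocol*

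**What the plan says.** Assignment: the Blinding sections of both documents (Protocol 7.1.2.3, SAP 1.4) say "Within each study site, participants will be assigned to study treatment according to a list". The synopsis plans for "Approximately 30 sites in the US". SAP 1.3, the section on randomisation itself, says only "Participants will be randomized in a 1:1:1 ratio to receive one of 3 lots of the study vaccine" through an interactive web system. Neither document names a stratification factor or a block size. That detail is left to a randomisation specification which is not part of the documents.

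Analysis: Protocol 9.3.2 defines the primary ANCOVA "with the study vaccine group as the fixed effect and the ELISA unit at Day 1" as covariate. The SAP 7.1.1 code is `model log(IgG) = log(IgG_D0) Group`, and SAP 11.2 confirms that the between-lot ratios "will be adjusted for pre-vaccination titer/ELISA unit". No model in either document contains site.

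Sample size (Protocol 9.1, SAP 1.2): the SD is an 80% upper confidence bound, "Day 29 IgG SD in log10 scale of 0.39". The planned lot difference is given as "Assuming 10% variation (lot-to-lot GMEU ratio is 1.1"). This leads to 248 evaluable per lot, 97% power per pair and about 90% for all three pairs. Success requires every pairwise 95% interval to lie inside 0.67 to 1.5.

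**The concern.** A factor used to organise assignment is normally carried into the analysis. When lots are balanced inside each site, differences between sites cancel from the lot contrasts. A model without site still counts that variance as residual noise, so its standard error is larger than the true sampling error of the contrast.

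Width matters here because success depends on fitting three intervals inside fixed limits. Site differences are plausible. Protocol 5.3 admits several prior vaccine histories, with a minimum of 6 months since the last dose and no maximum. Protocol 5.4 excludes confirmed infection only within the previous 4 months. These features could cluster by site, and a single Day 1 IgG value need not capture all of them. What is at stake is efficiency, not validity.

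**Working it through.** **Inputs.** From the documents: SD 0.39 (log10), n = 248 per lot, ratio 1.1, limits 0.67 to 1.5, two-sided 95% intervals, about 30 sites. Assumed: the site share s of residual Day 29 log10 IgG variance after baseline adjustment, taken as 0, 0.02, 0.05 and 0.10. The value 0.39 is used as the total residual SD. The relative change in width does not depend on that choice.

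**1. The plan's own figure.**

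- SE of a lot difference = 0.39 × √(2/248) = 0.03502.
- log10(1.5) − log10(1.1) = 0.17609 − 0.04139 = 0.13470.
- Power = Φ(0.13470/0.03502 − 1.965) = Φ(1.88) = 97.0%. The lower limit adds almost nothing to the failure probability.
- Three pairs: 0.97³ = 91.3%, consistent with about 90%.

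The plan reproduces with no site term.

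**2. Width, if lists are balanced within site.** Adding site reduces the residual SD to 0.39 × √(1 − s). The half-width without site is 1.963 × 0.03502 = 0.0688 on the log10 scale, a factor of 1.17. The 29 extra site terms barely move the t critical value (740 to 711 degrees of freedom).

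| s | Width ratio √(1 − s) | Half-width with site, as a factor |
|---|---|---|
| 0 | 1.000 | 1.172 |
| 0.02 | 0.990 | 1.170 |
| 0.05 | 0.975 | 1.167 |
| 0.10 | 0.949 | 1.162 |

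**3. Coverage of the planned interval.** With balanced lists the true SE is 0.03502 × √(1 − s), while the model without site uses 0.03502. Coverage is 2Φ(1.96/√(1 − s)) − 1: 95.2%, 95.6% and 96.1% at s = 0.02, 0.05 and 0.10. The error is in the conservative direction.

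**4. Power per pair at ratio 1.1, balanced lists.** Let SEs = 0.03502 × √(1 − s).

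- Without site: Φ((0.13470 − 1.965 × 0.03502)/SEs).
- With site: Φ(0.13470/SEs − 1.965).

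| s | Without site | With site |
|---|---|---|
| 0 | 97.0% | 97.0% |
| 0.02 | 97.1% | 97.3% |
| 0.05 | 97.3% | 97.6% |
| 0.10 | 97.6% | 98.2% |

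Even against the planned 97.0%, the gain is at most about 1.2 points.

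**5. All three pairs, lots at 1:1:1.1, perfect balance (simulated).** Overall success without and with site was 93.8% and 93.7% (s = 0), 94.0% and 94.3% (0.02), 94.4% and 95.0% (0.05), 94.9% and 96.1% (0.10).

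**6. Which form of site term.** Trials were simulated with 30 unequal sites and 248 evaluable per lot, with and without balanced lists (blocks of 6, assumed). Mean log10 half-width, without to with site:

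| s | Fixed site, balanced lists | Fixed site, lists not balanced | Random intercept, lists not balanced |
|---|---|---|---|
| 0 | 0.0687 to 0.0688 | 0.0687 to 0.0701 | 0.0688 to 0.0687 |
| 0.02 | 0.0688 to 0.0682 | 0.0687 to 0.0694 | 0.0687 to 0.0684 |
| 0.05 | 0.0686 to 0.0670 | 0.0685 to 0.0683 | 0.0686 to 0.0676 |
| 0.10 | 0.0686 to 0.0653 | 0.0686 to 0.0665 | 0.0686 to 0.0661 |

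With balanced lists the random intercept gave 0.0687 to 0.0685 at s = 0 and 0.0686 to 0.0653 at s = 0.10. Fixed effects can widen the interval when lists are not balanced and sites differ little. The random intercept did not widen it in these runs.

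**The case against.** The strongest reply is that neither condition for a loss is documented. A list used within each site is not described as stratified, blocked or balanced. The sentence stands in the blinding sections, while the allocation sections mention no strata. No between-site variance is given either, and Day 1 IgG may already absorb much of what differs between sites. The eligibility limits on recent vaccination and infection also narrow those differences. All of this stands, so the point can only be conditional.

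The planned model is also prespecified, agrees across both documents, and errs on the safe side if it errs at all. That stands too. The documents themselves expect 262 per lot against the 248 required, which leaves some headroom.

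A reader might infer that omitting site leaves the trial with only about 75% overall success. The documents do not support that. Figures of that size arise when the lots are spread at 1:1.1:1.21, so that one pair differs by 1.21, whereas the plan assumes 1.1. An equivalent spread, with lots 10% above and below a middle lot, gives 73.6% with no site effect in the simulation at all. The low figure therefore comes from the spread of the lots and not from the missing term.

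The remaining objection is that a site term adds choices to the primary analysis for a gain that may be nil. This has force against fixed effects, which need a pooling rule for small sites and can widen the interval. It has little force against a single random intercept.

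**Conclusion.** The point holds as a minor, conditional matter of efficiency. If lists balance lots within site and sites differ after baseline adjustment, the intervals are wider than needed by about 1% to 5% over assumed site shares of 0.02 to 0.10. At a share of 0 nothing is lost. With lots at 1:1:1.1, overall success would rise by about 1 point at a share of 0.10 and by less below that.

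Two stronger readings should be set aside. It is not established that the intervals are too wide, because both within-site balance and between-site variance are assumptions. Nor does the omission weaken the equivalence claim or the sample size: with balanced lists coverage is at or slightly above 95%, and 248 per lot with 97% pairwise power reproduces with site left out.

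**What to change.** Before unblinding:

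- Add site as a random intercept to the IgG model in SAP 7.1.1, for example `random intercept / subject=Site;` in the PROC MIXED step already planned. Do the same for the MN50 and hACE2 models, and update SAP 11.2 and Protocol 9.3.2 to match.
- Keep the model without site as a named sensitivity analysis.
- Prefer the random intercept to fixed site effects, for the reasons in the last table of the working.
- State in SAP 1.3 whether randomisation is stratified by site. If the sponsor prefers to leave site out, give the reason.

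The cost is one model statement, one sentence in SAP 1.3 and one extra variance component to estimate. If sites do not differ, there is no gain.
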